5.3 Rationale for the Present Study

Although there is evidence of efficacy and safety of solithromycin in adults, the safety and efficacy of solithromycin have not been established in children. There is evidence of similarities in children and adults in 1) CABP definitions and pathophysiology, 2) causative organisms, 3) response to intervention and 4) exposure-response relationship. Therefore, extrapolation of efficacy in pediatric subjects from adult clinical trial efficacy data is reasonable. A safety study in pediatric subjects with CABP, however, is needed to compare the safety and tolerability of solithromycin to comparators. The proposed study will gather necessary safety data and, as a secondary objective, provide an assessment of solithromycin efficacy as CABP treatment in pediatric subjects.

5.4 Rationale for the Dosage Regimen

[figure not shown]
The dosing regimens to be studied are intended to provide therapeutic solithromycin exposures against CABP, as efficacy in pediatric subjects with CABP will be extrapolated from the results in the phase 3 adult CABP trials. The dosing regimens for each age group and each of the 3 formulations (capsule, IV infusion, and suspension) were determined in phase 1 studies in children.

Data from two phase 1 studies in children (N=92) were merged and used to develop a population PK model that informs dosing for this study for all formulations. A two compartment model with linear elimination characterized the solithromycin data following both oral (capsule and suspension) and intravenous administration. To account for the growth effects, actual body weight was included in the model using allometric scaling. Using the final model, Monte Carlo simulations were performed to identify pediatric dosing that matches adult exposure (area under the concentration versus time curve from 0 to 24 hours and maximal drug concentrations after multiple doses) observed in the phase 3 program.

The selected dosing regimen for adolescents (12-17 years) receiving solithromycin via oral administration (capsules or suspension) was 800 mg on Day 1 and 400 mg on Days 2-5 if they weigh ≥ 40 kg. For subjects 12 to 17 years and <40 kg, a capsule dosing regimen of 20 mg/kg on

Day 1 (800 mg maximum) and 10 mg/kg on Days 2-5 (400 mg maximum) was selected based on simulated exposure (Figure 2). Suspension dosing for adolescents was selected based on data obtained from a bioequivalence study in adults between capsules and suspension and the similar bioavailability estimates obtained for both formulations in the population PK model.

[figure not shown]
Figure 2 Simulated Day 5 Exposure following a Capsule Dose of 20 mg/kg on Day 1 and 10 mg/kg on Days 2-5.

Note: Doses rounded upward to the nearest 200 mg. The dashed line represents an adult Day 4 AUC₀₋₂₄ of 12.6 mcg*h/mL.

For the suspension dosing for children <12 years of age, a dose of 20 mg/kg on Day 1 (800 mg maximum) and 10 mg/kg on Days 2-5 (400 mg maximum) resulted in a comparable simulated Day 5 AUC₀₋₂₄ across pediatric age groups (Figure 3). Although the median simulated exposure appears to be lower in the 0-2 years age group, the simulated exposure was within the range observed in adults and it's possible that the observed values may be higher due to immature CYP3A4 metabolism in this age group.

Figure 3 Simulated Day 5 Exposure following a Suspension Dose of 20 mg/kg on Day 1 and 10 mg/kg on Days 2-5

Note: The dashed line represents an adult Day 4 AUC_{0-24} of 12.6 mcg*h/mL. There is only one subject in the 2-6 years ≥ 40 kg category

Intravenous daily dosing of 8 mg/kg resulted in comparable simulated Day 5 AUC_{0-24} across all pediatric age groups: median (standard deviation) 14.4 mcg*h/mL (23.4) for 12-17 years; 14.1 mcg*h/mL (25.4) for 6-<12 years; 11.0 mcg*h/mL (26.0) for 2-<6 years; and 9.4 mcg*h/mL (19.1) for 0-<2 years. The adult exposure used for matching purposes was 12.6 mcg*h/mL.

Because of the complete efficacy extrapolation approach to determination of efficacy in the pediatric population, the duration of study drug regimens are the same as those in adults. Oral-only dosing is for 5 days intravenous-only and IV-to-oral dosing are for 7 days duration.

5.5 Rationale for the Comparator

Comparators were selected following review of the Pediatric Infectious Diseases Society/Infectious Diseases Society of America guidelines for empiric therapy of CABP (Bradley 2011), recent publications on CABP therapy in children (Aurangzeb 2003; Kogan 2003; Bradley 2007; Awashti 2008; Ribeiro 2011; Lodha 2013), and the most recently conducted trials of CABP in children listed on ClinicalTrials.gov (www.clinicaltrials.gov). The group of acceptable

comparator drugs was selected to include drugs commonly used per standard of care in both the U. S. and at international sites participating in this trial.

6 STUDY OBJECTIVES

Primary

- Evaluate the safety and tolerability of solithromycin in adolescents and children with CABP

Secondary

- Evaluate the efficacy of solithromycin in adolescents and children with CABP
- Evaluate the population PK of solithromycin in adolescents and children with CABP

7 STUDY DESIGN

This is a phase 2/3, randomized, open-label, active-control, multi-center study to assess the safety and efficacy of solithromycin in children and adolescents with CABP. Approximately 400 subjects (~300 in the solithromycin group and ~100 in the comparator group) will be enrolled. Randomization will be stratified by age group (12 through 17 yo, 6 to <12 yo, 2 to <6 yo, and 2 months to <2 yo). At least 40 subjects will be randomized into each age group.

Subjects who meet all inclusion/exclusion criteria and sign the informed consent/assent will be enrolled. Subjects will be randomized to receive solithromycin or a comparator antibiotic, administered IV and/or by mouth (PO) based on weight and age. Subjects will be treated daily for 5 to 7 days with oral solithromycin and 5 to 7 days with IV or IV-to-oral solithromycin. Subjects will be treated for 5 to 10 days with comparator antibiotics. Subjects will have safety and efficacy assessments during and after treatment.

7.1 Duration of Subject Participation

The duration of subject participation from signing the informed consent form (ICF) will be approximately 32 days (includes up to 10 days of study drug/comparator drug administration, a follow-up visit at 16 days [\pm 4 days] after randomization, AE monitoring for 16 (\pm 4) days, and SAE monitoring for 28 (\pm 4) days post-randomization). Adverse event monitoring 28 days after randomization can be conducted by telephone/other media visit. The study duration from first subject first visit until last subject last visit will be approximately 24 months.

7.2 Number of Subjects

Approximately 400 subjects \geq 2 months to 17 years of age, inclusive, will be enrolled as follows:

- Age Group 1: Adolescents from 12 years to 17 years, inclusive
- Age Group 2: Children from 6 years to <12 years
- Age Group 3: Children from 24 months to <6 years
- Age Group 4: Infants from \geq 2 months to <24 months

A minimum of 40 subjects will be enrolled in each age group. Approximately 20% of subjects will be enrolled at U.S. centers.

7.3 Study Drug Dosage and Administration

Solithromycin will be administered IV or PO according to Table 5 through Table 8 below. If dosing begins with oral therapy, the Day 1 dose will be a loading dose. No loading doses are used with IV solithromycin administration or if switched to oral administration. An IV-to-PO switch can occur after the first IV dose. Subjects starting with oral therapy will receive 5 days of solithromycin treatment, and those starting with IV therapy (regardless of if and when they switch to oral therapy), will receive 7 days of solithromycin treatment.

For subjects receiving the capsule formulation, 200 mg solithromycin capsules will be used to provide the absolute dose of either 200 mg, 400 mg, or 800 mg. The capsule dose will be rounded upwards to the nearest 200 mg, not to exceed an 800 mg loading dose and 400 mg maintenance dose. Study drug should be swallowed with water approximately every 24 hours and at approximately the same time each day (± 4 hours). Study drug can be taken without regard to food.

Table 5 Capsule Dosing Regimens

Age (years)	Weight	Route	Formulation	Day 1 (Max dose: 800 mg)	Days 2 to 5 (Max dose: 400 mg)
6 to 17	>30 kg	PO	Capsules	800 mg	400 mg
	>20 to 30 kg	PO	Capsules	600 mg	400 mg
	≤ 20 kg	PO	Capsules	400 mg	200 mg

Subjects requiring an oral dosage form other than capsules will receive suspension formulation, provided at 275 mg/5 mL strengths, to achieve the age-appropriate mg/mL and solithromycin dose. Any dosing variations within 10% of the calculated suspension dose is not considered a deviation.

Table 6 Suspension Dosing Regimens

Age (years)	Route	Formulation	Day 1 (Max dose: 800 mg)	Days 2 to 5 (Max dose: 400 mg)
12 to 17	PO	Suspension	20 mg/kg (800 mg)	10 mg/kg (400 mg)
6 to <12	PO	Suspension	20 mg/kg	10 mg/kg
2 to <6	PO	Suspension	20 mg/kg	10 mg/kg
2 mo to <2	PO	Suspension	20 mg/kg	10 mg/kg

No loading doses are used with IV solithromycin administration. Intravenous solithromycin should be infused over approximately 60 minutes (± 20 minutes) approximately every 24 hours (± 4 hours). Changes to the infusion duration should be discussed with the study medical monitor prior to study drug administration. Any dosing variations within 10% of the calculated IV dose is not considered a deviation.

Table 7 Intravenous Dosing Regimens

Age (years)	Route	Formulation	Days 1 to 7 (Maximum dose: 400 mg)
12 to 17	IV	Solution	8 mg/kg
6 to <12	IV	Solution	8 mg/kg
2 to <6	IV	Solution	8 mg/kg
2 mo to <2	IV	Solution	8 mg/kg

A subject can be converted from the IV to an oral formulation following 1 or more IV doses. The first oral dose will be 10 mg/kg with a maximum of 400 mg.

Table 8 Intravenous to Oral Dosing Regimens

Age (years)	Route	Oral Formulation	Day 1 to Last IV Dosing Day (Max dose: 400 mg)	First Oral Dosing Day to Day 7 (Max dose: 400 mg) ^a
12 to 17	IV/PO	Suspension or Capsules	8 mg/kg	10 mg/kg (400 mg)
6 to <12	IV/PO	Suspension or Capsules	8 mg/kg	10 mg/kg
2 to <6	IV/PO	Suspension	8 mg/kg	10 mg/kg
2 mo to <2	IV/PO	Suspension	8 mg/kg	10 mg/kg

- a. The adult dose should be administered unless the subject weighs <40 kg, in which case they receive 10 mg/kg on the first oral dosing day through Day 7. The capsule dose is rounded upwards to the nearest 200 mg.

Comparator drug:

Comparators will be selected according to age and are consistent with current recommendations for treatment of CABP in children. A dosing table is provided below.

Children ≥2 months to <5 years of age:

- a. Ceftriaxone IV **OR**
- b. Ampicillin IV **or** amoxicillin IV **OR**
- c. Amoxicillin-clavulanic acid PO **or** IV **or** amoxicillin PO

Children 5 to 17 years of age (inclusive):

- a. Ceftriaxone IV **OR**
- b. Ampicillin IV **or** amoxicillin IV **OR**
- c. Amoxicillin-clavulanic acid PO **or** IV **or** amoxicillin PO

Azithromycin IV/PO or erythromycin lactobionate IV or erythromycin PO may be added to any of three treatment regimens above. Azithromycin is also acceptable as a first line of treatment.

Table 9 Recommended Comparator Regimens

	United States	Rest of the World
Amoxicillin	45-90 mg/kg/day orally in 2 or 3 divided doses; not to exceed 3 g/day	45-90 mg/kg/day orally in 2 or 3 divided doses; not to exceed 3 g/day 50-100 mg/kg/day intravenously in equally divided doses every 6 hours
Amoxicillin-clavulanic acid (oral)	Children <40 kg: amoxicillin component 90 mg/kg/day orally in divided doses given every 12 hours [4000 mg/day max dose] Children ≥40 kg, 875 mg orally every 12 hours or 500 mg orally every 8 hours [4000 mg/day max dose]	Children <40 kg: 20 mg/5 mg/kg/day to 60 mg/15 mg/kg/day given orally every 8 hours Children ≥ 40 kg: One 500 mg/125 mg dose given orally every 8 hours
Amoxicillin-clavulanic acid (IV)	-	Children >4kg but< 40kg: amoxicillin component 25 mg/kg intravenously every 8 hours [1000 mg max dose] Children ≥ 40 kg: amoxicillin component 1000 mg intravenously every 8 hours
Ampicillin	150-200 mg/kg/day intravenously in equally divided doses every 6 hours	-
Azithromycin	10 mg/kg intravenously/orally on day 1 [500 mg maximum dose] followed by 5 mg/kg orally every 24 hours [250 mg maximum dose]	10 mg/kg orally on day 1 [500 mg maximum dose] followed by 5 mg/kg orally every 24 hours [250 mg maximum dose]
Ceftriaxone	50-75 mg/kg/day intravenously in equally divided doses every 12 hours; total daily dose should not exceed 2 g	50-80 mg/kg intravenously once daily
Erythromycin	40 mg/kg/day orally every 6 hours	30-50 mg/kg/day orally every 6 hours
Erythromycin lactobionate	15 to 20 mg/kg/day intravenously in equally divided doses every 6 hours	50 mg/kg/day intravenously/orally in equally divided doses every 6 hours

Note: if doses of comparator drugs noted in the dosing table above differ those prescribed per standard of care, a site can use the locally prescribed dose.

IV-to-PO switch:

Subjects receiving an IV comparator drug (i.e., ceftriaxone, ampicillin) in any age group may be switched to oral treatment using amoxicillin-clavulanic acid PO (amoxicillin component, 45 mg/kg every 12 hours; subjects weighing ≥40 kg, 875 mg every 12 hours or 500 mg every 8 hours) or amoxicillin alone (45 mg/kg every 12 hours, up to a maximum of 4 g/day).

Subjects must receive 5 to 10 days of treatment with comparator. The exact duration of treatment may be determined at the investigator's discretion.

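### The list of capsule doses in Protocol 7.3 (200, 400 or 800 mg) omits the 600 mg Day 1 dose that Table 5 gives for subjects over 20 to 30 kg

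*Protocol*

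**What the plan says.** Protocol 7.3 opens by naming its dosing source: "Solithromycin will be administered IV or PO according to Table 5 through Table 8 below". The paragraph on capsules then states that "200 mg solithromycin capsules will be used to provide the absolute dose of either 200 mg, 400 mg, or 800 mg", and continues: "The capsule dose will be rounded upwards to the nearest 200 mg, not to exceed an 800 mg loading dose and 400 mg maintenance dose".

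Table 5 follows directly. For ages 6 to 17 it has three weight rows. The middle row reads ">20 to 30 kg PO Capsules 600 mg 400 mg", that is, 600 mg on Day 1 and 400 mg on Days 2 to 5. The capsule tables in the Synopsis and in SAP 3.4 carry the same row.

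Three other provisions bear on the point:

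- The 10% dosing tolerance in Protocol 7.3 and SAP 3.4 covers suspension and IV doses, not capsules.
- Protocol 12.1.3 defines an overdose by reference to the dose that the protocol sets, and has it forwarded in the same time frame as a serious adverse event.
- SAP Sections 7 and 9 provide for a summary and listing of major protocol deviations, and for a per-subject exposure listing with weight-adjusted dose and loading-dose information.

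**The concern.** A closed list of absolute doses and a dosing table should contain the same doses. Here the table contains one that the list excludes, and it is the Day 1 dose for an entire weight band. Read literally, the two statements cannot both be followed for a subject in that band who starts on capsules.

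Day 1 matters because it is the loading dose for oral starters, and Protocol 5.2.4.1 reports evidence that ALT elevation is related to exposure. Capsules have no tolerance margin to absorb a discrepancy. Deviation and overdose are both judged against what the protocol specifies, so the specification should be a single one.

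**Working it through.** **1. Compare the two sets of doses.**

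| Source | Capsule doses |
|---|---|
| Sentence in Protocol 7.3 | 200, 400, 800 mg |
| Table 5, ≤20 kg | 400 mg Day 1; 200 mg Days 2 to 5 |
| Table 5, >20 to 30 kg | 600 mg Day 1; 400 mg Days 2 to 5 |
| Table 5, >30 kg | 800 mg Day 1; 400 mg Days 2 to 5 |

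The Table 5 set is {200, 400, 600, 800}. Removing the doses in the sentence leaves {600}. That dose appears in one cell only: Day 1, >20 to 30 kg.

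**2. Check the other places that give this cell.** The Synopsis and SAP 3.4 both show 600 mg. No current passage assigns 400 or 800 mg on Day 1 to this band.

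**3. Check Table 5 against the rounding rule.** The capsule paragraph gives a rounding step and caps, but no mg/kg figure. Protocol 5.4 supplies one ("a capsule dosing regimen of 20 mg/kg on" Day 1, then 10 mg/kg on Days 2 to 5), stated in the text for ages 12 to 17 under 40 kg. Applying it to all of ages 6 to 17 is an assumption. Under it:

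dose = min(cap, 200 × ceil(rate × weight / 200)), with rate 20 mg/kg and cap 800 mg on Day 1, and rate 10 mg/kg and cap 400 mg on Days 2 to 5.

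- 20 kg: 20 × 20 = 400, gives 400 mg; 10 × 20 = 200, gives 200 mg.
- 20.1 kg: 402 rounds up to 600 mg; 201 rounds up to 400 mg.
- 30 kg: 600 gives 600 mg; 300 rounds up to 400 mg.
- 30.1 kg: 602 rounds up to 800 mg; 301 rounds up to 400 mg.

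On a 0.1 kg grid from 10.1 to 90 kg this reproduces every cell of Table 5, with no mismatch. So Table 5 is consistent with the rounding rule under the stated assumption, and the sentence is the statement that stands apart.

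**4. Check what else is affected.** The Days 2 to 5 dose for this band, 400 mg, is in the list. After an IV-to-oral switch (Table 8), capsules are rounded up to a multiple of 200 mg with a 400 mg maximum, so only 200 or 400 mg can arise, and both are listed. The conflict is confined to Day 1 of oral-start capsule dosing in one band.

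**5. Size a hypothetical substitution.** If a listed neighbour replaced 600 mg: 400/600 = 0.67, a change of -33%; 800/600 = 1.33, a change of +33%. In mg/kg (dose divided by weight):

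| Weight | 400 mg | 600 mg | 800 mg |
|---|---|---|---|
| 20.1 kg | 19.9 | 29.9 | 39.8 |
| 25 kg | 16.0 | 24.0 | 32.0 |
| 30 kg | 13.3 | 20.0 | 26.7 |

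The documents give no weight distribution, so the number of subjects in the band is unknown.

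**The case against.** The best defence is that the sentence is an incomplete list of capsule multiples and not a rival instruction. It assigns no dose to any weight, so nobody can dose a child from it. A site has to use Table 5, which the section names as its source and prints a few lines below. The 600 mg entry is three whole 200 mg capsules, and every place that assigns a Day 1 capsule dose to this band agrees on it. Any off-table dose would show in the per-subject exposure listing. The SAP also records that the trial was terminated in March 2018 with under a quarter of the planned enrolment, so a letter to pharmacies would change little.

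All of this stands, and it rules out several stronger readings that a reader might infer:

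- That a site cannot give the tabulated dose. It can, by following the table the section points to.
- That the protocol states two competing Day 1 doses for the band. It states one, next to a list that leaves it out.
- That the trial data contain 33% dose scatter. Nothing in the documents shows this; it would need a site to disregard the weight row.
- That the rounding rule alone yields 600 mg. It does so only with the 20 mg/kg basis carried over from 5.4.
- That safety and PK are reported on a single 6 to 17 year capsule cohort. SAP Table 3 separates 12 to 17 from 6 to <12 years. A combined 6 to 17 group split by formulation appears only in the laboratory figures, and the PK analysis follows an appended plan that is not in the text reviewed.

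The defence does not make the sentence consistent with the table. An either/or list that excludes a tabulated loading dose is wrong as written.

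**Conclusion.** The point holds, at low severity. The list in 7.3 omits exactly one of the four doses in Table 5, and that dose is the Day 1 capsule dose for everyone aged 6 to 17 weighing over 20 to 30 kg. This needs no assumption: it follows from comparing the sentence with the table, the Synopsis and SAP 3.4. The agreement of Table 5 with the rounding rule does rest on an assumption, namely that the 20 and 10 mg/kg basis applies across ages 6 to 17.

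The 33% difference either way is an upper bound on a hypothetical error, not an expected effect. Sample size, endpoints and error rates are untouched. What remains of practical weight is that exposure, deviation and overdose judgements for this band should rest on one unambiguous reference dose.

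**What to change.** Reconcile the sentence in Protocol 7.3 with Table 5, the Synopsis and SAP 3.4 so that all four state the same set of capsule doses. The sponsor decides which set is intended. Use it as the single reference for the study drug exposure listing, the major protocol deviation listing and overdose reporting under Protocol 12.1.3, and say so in the clinical study report.

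The cost is one sentence of wording and a check that the listings use the agreed reference. With enrolment closed, the benefit lies in clean listings and in any later reuse of this dosing text.

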12.1.3 Other Reportable Events

Reports of overdose (with or without an AE), inadvertent or accidental exposure, and known pregnancy should be forwarded in the same time frame as an SAE.

Overdose occurs when a subject is administered or has taken a dose greater than the intended or scheduled dose specified by the protocol.

All pregnancies occurring during the study must be followed for information regarding the course of pregnancy, delivery, and condition of the newborn. Follow-up should be provided by the investigator to the medical monitor in a timely manner.

Monitoring of liver laboratory tests

Monitoring of liver laboratory tests of special interest (AST, ALT, and direct bilirubin) will be conducted throughout the study. Three levels of monitoring will be performed:

Weekly monitoring: Each week, data entered in the eCRF will be downloaded to identify any child enrolled in the study with a) normal AST, ALT, or direct bilirubin at baseline AND at least $2 \times \text{ULN}$ on any of these laboratory tests at any study visit post baseline and b) any child meeting laboratory criteria for Hy's Law. These data will be provided to the DCRI medical monitor and the sponsor for review.

Quarterly monitoring: Each quarter, summary data of children enrolled in the study with a) normal AST, ALT, or direct bilirubin at baseline AND at least $3 \times \text{ULN}$ on any of these laboratory tests at any study visit post baseline and b) any child meeting laboratory criteria for Hy's Law will be provided to the DMC chair for review. Actions by the DMC chair will be described in the DMC meeting minutes.

Biannual monitoring: Twice per year, all data pertaining to liver laboratory tests will be presented to the DMC for review. This includes the data presented quarterly as well as listings of all laboratory tests at every visit.

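### The comparator IV-to-oral switch text conflicts with Table 9: oral amoxicillin has two daily maxima, and the amoxicillin-clavulanate dose has no regional split

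*Protocol*

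**What the plan says.** **Oral amoxicillin.** Table 9 (Protocol Section 7.3) gives 45 to 90 mg/kg/day "in 2 or 3 divided doses; not to exceed 3 g/day", with identical entries for the United States and the rest of the world. The IV-to-oral switch paragraph after the table gives amoxicillin alone as a 12-hourly dose of 45 mg/kg, "up to a maximum of 4 g/day".

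**Oral amoxicillin-clavulanate.** The switch paragraph gives one regimen without naming a region: "amoxicillin component, 45 mg/kg every 12 hours; subjects weighing ≥40 kg, 875 mg every 12 hours or 500 mg every 8 hours". Table 9 does split by region:

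- United States, below 40 kg: 90 mg/kg/day of the amoxicillin component. From 40 kg: 875 mg every 12 hours or 500 mg every 8 hours. Both carry a 4000 mg/day maximum.
- Rest of the world: "Children <40 kg: 20 mg/5 mg/kg/day to 60 mg/15 mg/kg/day given orally every 8 hours" and "Children ≥ 40 kg: One 500 mg/125 mg dose given orally every 8 hours".

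**Scope of the switch rule.** It covers every age group. Section 7.3 cites ceftriaxone and ampicillin as the IV drugs, and ceftriaxone has a rest-of-world regimen in Table 9. The Synopsis version applies to any IV comparator.

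**Local doses.** A note between the table and the switch paragraph lets a site use its own prescribed dose where that differs from the dosing table.

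**Overdose.** Section 12.1.3 states: "Overdose occurs when a subject is administered or has taken a dose greater than the intended or scheduled dose specified by the protocol". Overdoses are to be reported on the SAE timetable, with or without an adverse event.

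The Synopsis repeats the table, the note and the switch paragraph, with the same mismatches. SAP Section 3.4 has the treating provider choose the comparator drug and dose from those listed in the protocol, taking account of weight and region.

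**The concern.** Two stated maxima for one oral drug cannot both hold, and nothing suggests that a higher ceiling after an IV start was intended. For amoxicillin-clavulanate, the protocol distinguishes regions in the table and then drops the distinction in the paragraph that governs the switch.

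The practical question is classification. A heavier child who switches to amoxicillin at a dose between 3 and 4 g/day is within one passage and above the other. The same holds for a rest-of-world child below 40 kg who switches to amoxicillin-clavulanate at the paragraph's dose. Sites and monitors could record the same dose as compliant, as a deviation or as a reportable overdose. Safety is the primary objective and SAP Section 7 summarises and lists major protocol deviations, so comparator dosing should have a single reference.

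**Working it through.** This is unit conversion only. Daily dose = dose per administration × administrations per day. Weight at which a cap binds = cap ÷ (mg/kg/day). No sample size, power or error rate is involved.

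**Switch dose, both drugs.** 45 mg/kg × 2 = 90 mg/kg/day.

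**Amoxicillin alone, compared at 90 mg/kg/day.**

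- 3 g cap: 3000 ÷ 90 = 33.3 kg.
- 4 g cap: 4000 ÷ 90 = 44.4 kg.

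| Weight (kg) | Uncapped, mg/day | Table 9, mg/day | Switch text, mg/day | Difference |
|---|---|---|---|---|
| 30 | 2700 | 2700 | 2700 | 0 |
| 35 | 3150 | 3000 | 3150 | 150 (5%) |
| 40 | 3600 | 3000 | 3600 | 600 (20%) |
| 45 | 4050 | 3000 | 4000 | 1000 (33%) |
| 60 | 5400 | 3000 | 4000 | 1000 (33%) |

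The passages agree up to 33.3 kg. The gap then widens to 1 g/day at 44.4 kg and stays there. Subjects up to 17 years are eligible, so such weights can be expected.

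**Amoxicillin-clavulanate below 40 kg (amoxicillin component).**

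- Against the US column: 90 against 90 mg/kg/day, so they agree.
- Against the rest-of-world range of 20 to 60 mg/kg/day: 90 ÷ 60 = 1.5 times the upper limit and 90 ÷ 20 = 4.5 times the lower limit.
- Example at 20 kg: 90 × 20 = 1800 mg/day, against 20 × 20 = 400 to 60 × 20 = 1200 mg/day.
- The interval also differs: every 12 hours in the switch text, every 8 hours in the rest-of-world entry.

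**Amoxicillin-clavulanate from 40 kg.** The rest-of-world entry is 500 × 3 = 1500 mg/day.

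- Switch option 1: 875 × 2 = 1750 mg/day, and 1750 ÷ 1500 = 1.17, or 17% higher.
- Switch option 2: 500 × 3 = 1500 mg/day, which agrees.
- Both options appear in the US column, so there is no conflict there.

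The rest-of-world range is read as printed, as a total per day given in 8-hourly doses.

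**The case against.** The strongest reply is that comparator doses were never meant as rigid limits. Table 9 is titled as recommended regimens, the switch sentence is permissive, and sites may use local doses. Section 9.2 refers to local availability and treatment preferences, and Section 8.3.1 asks that oral step-down on comparator be guided by susceptibility testing. Both switch drugs also appear in Table 9, so the local-dose note can be read as reaching them.

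Much of this stands, and it limits the practical effect. It does not remove the conflict. Both passages use the language of a limit. The note refers to the dosing table and comes before the switch paragraph, so its reach is uncertain. Even read generously, it lets a site depart from the protocol without saying which protocol figure is being departed from. Section 9.2 itself points back to the doses given earlier.

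A reader might go further and infer that a child dosed under one passage meets the overdose definition. The documents do not support that. A dose that the switch paragraph permits is arguably specified by the protocol, and a child held to 3 g/day is below the switch ceiling. Overdose status is ambiguous, not established. That spurious comparator reports would follow is conjecture. An overdose report needs no adverse event, so it would not by itself enter the primary endpoints.

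A reader might also note that about 20% of subjects are planned in the US and take the other 80% as affected. That is the planned non-US share of the whole trial. The issue reaches only the comparator arm (one in four), then only those who start IV and switch to one of these two drugs, and then only certain weights. The documents do not give that number.

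**Conclusion.** The point holds as a minor internal contradiction in comparator dosing, present in both Section 7.3 and the Synopsis. Its two parts differ in kind. The amoxicillin caps conflict in every region, but only above 33.3 kg at 90 mg/kg/day. The amoxicillin-clavulanate mismatch is a missing regional qualifier. It does not arise in the US, and the 1.5-fold excess must not be carried over to children of 40 kg or more.

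No endpoint, analysis or sample-size figure changes. The SAP (Section 2) records termination in March 2018 with fewer than a quarter of the planned 400 enrolled, that is, fewer than 100. If the planned 3:1 ratio held, that means fewer than about 25 comparator subjects, and fewer still who switched. What remains of value is consistent classification of deviations and overdoses in the report, and correct text if the protocol is reused.

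The conclusion rests on reading the rest-of-world range as a daily total and on the switch paragraph applying in all regions, since it names none.

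**What to change.** Reconcile the IV-to-oral switch paragraph with Table 9, by region, in Section 7.3 and the Synopsis, so that each oral drug has one stated daily maximum or an explicit reason for two. State whether the local-dose note also covers the switch. State how a comparator dose that one passage permits and the other exceeds is to be classified under Section 12.1.3. Which dose or cap applies is for the sponsor to settle.

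The cost is protocol wording only. As the trial has ended, the remaining step for this study is to state in the clinical study report which reference was used to classify comparator doses after a switch.
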